3. INTRODUCTION/BACKGROUND MATERIAL/PRELIMINARY STUDIES AND SIGNIFICANCE

- *Describe and provide the results of previous work by yourself or others, including animal studies, laboratory studies, pilot studies, pre-clinical and/or clinical studies involving the compound or device to be studied.*
- *Include information as to why you are conducting the study and how the study differs from what has been previously researched, including what the knowledge gaps are.*
- *Describe the importance of the knowledge expected to result*

This project represents a pilot project under the umbrella of the NIH-funded grant “Re-engineering precision therapeutics through N-of-1 trials” (Northwell IRB 19-0572-MRB) which is funded to test use cases appropriate for N-of-1 methodology and evaluate them for acceptability and scalability.

The overarching objective of our parent grant is to develop, test, and implement an innovative technology platform for conducting N-of-1 trials that transforms precision therapeutics. Right now, clinicians are engaging in clinical encounters in which they are trying to determine the best therapy for individual patients. These encounters are likely to be unsuccessful. Clinicians rely on the best available evidence (e.g., results from parallel group, phase III randomized clinical trials; RCTs) for recommending therapies to a patient. Yet, conventional, between-group RCTs only provide estimates of the effect of therapies on the hypothetical ‘average’ patient in those trials. Individual patients, however, often respond differently than the hypothetical average patient in the phase III RCTs, and thus, heterogeneity of therapy response plagues clinical decisions made for an individual patient every day.

The most scientifically rigorous — and potentially transformative — method for determining optimal therapy for a patient is a single-patient (N-of-1) trial. N-of-1 trials are multiple crossover trials, usually randomized, and often masked, conducted within a single patient, with data collected objectively, continuously, and in the real-world, for a sufficient time period to determine whether the therapy, compared to a placebo or other active therapy, is optimal for a particular patient. They also yield information on off-target actions, such as side-effects or unintended consequences, so that a more complex picture can emerge about the overall

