Once potential participants successfully submit their signed consent form, they will receive an onboarding questionnaire to collect more information, including a home address. A Consenting Coordinator will review this information and send the potential participant a text which will include a confirmation of the start date of their baseline period, as well as a link to a short video of what to expect during onboarding to the study. They will be receive an initial study kit including a Fitbit device via mail, and will receive a copy of their electronically signed HIPAA authorization and consent form with a URL to view the informed consent video that they watched previously.

All baseline periods will begin on a Monday. No more than 20 participants will be permitted to begin on the same day. The baseline period will take place over the course of 2 weeks. Potential participants will not receive any melatonin or placebo pills during the baseline period, and they will be asked to refrain from taking any melatonin on their own. Participants will be instructed to continue treating their sleep quality issues as they normally would.

At three randomized times each day during waking hours (identified by the potential participant during their onboarding survey), baseline participants will receive a text message asking them to rate their pain, fatigue, concentration, confidence, mood, and stress levels at that exact moment. Each morning, baseline participants will receive a survey asking a few questions about their sleep quality the previous night using a modified version of the Consensus Sleep Diary, as well as factors that may have contributed to any sleep issues. At the end of the baseline period on Sunday evening, baseline participants will receive a slightly longer survey that includes the Insomnia Severity Index.

During the baseline period, potential participants will be asked to wear their Fitbit all day and night, even while they are sleeping. Participants will be asked to download the Fitbit app to their smart phone. Baseline participants will be instructed to sync their Fitbit device by opening the Fitbit app on their phone at least every two days and to charge their device at least every four days.

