During all intervention weeks (12 weeks total), participants will be asked to continue wearing their Fitbit device each day and night. They will continue to receive 3 randomized text message surveys each day with questions about their pain, fatigue, concentration, confidence, mood, and stress at that current moment, as well as a morning text asking them to report on their sleep quality the previous night, using a modified Consensus Sleep Diary. Morning surveys during the intervention weeks will also include questions about any melatonin or placebo-related side-effects the participant is experiencing. At the end of each intervention period on Sunday evening (every two weeks), participants will receive a slightly longer survey that includes the Insomnia Severity Index. A study phone number and email address will be available as part of each survey to contact the study team

if a participant is concerned about any side effects they are experiencing. Participants will be instructed to contact 911 or go to the nearest emergency room in the event of a medical emergency. In addition, participants will be advised to stop taking their pills if they are concerned about side effects.

Participants may receive additional text messages to those outlined above with important reminders about their protocol (e.g., transition to a new intervention period), or to remind participants to sync their data or charge their devices. We will send a maximum of 5 text message surveys per day during the study, as well as text messages of these reminders and other important study communications.

In the event of an unanticipated circumstance that temporarily prevents a participant from completing study activities (illness, injury, death in the family, etc.), the participant will have the option of pausing their study to resume once their circumstance has been positively resolved.

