Participants will complete remote data monitoring after they have gone through one baseline period (two weeks), two 3mg dose melatonin intervention periods (two weeks each), two 0.5mg dose melatonin intervention periods (two weeks each), and two placebo periods (two weeks each), or 14 weeks total. Alternatively, a participant may choose to withdraw from the study, or be withdrawn from the study by the research team. Upon completion of data monitoring, participants will be given instructions on how to un-link their Fitbit from the study account. Melatonin or placebo adherence tracking will be suspended, as will daily text messages and survey prompts.

We will compile the self-reported data from questionnaires, side effects, pain, fatigue, concentration, confidence, mood, and stress assessments, as well as information from the Fitbit regarding activity (steps, heart rate, flights climbed and intensity) and sleep (duration, estimated sleep stages) for each individual participant. Melatonin or placebo adherence will be tracked via a study dashboard connected to the pill bottle adherence device and will be included in the compiled data. No identifying information associated with participants will be provided to Nomi, the medication adherence device company, or included on the adherence report provided by Nomi. We will analyze this data and create a summary report of the participant's observed data over the study period, in relation to the 3mg melatonin, 0.5mg melatonin, and placebo intervention periods.

The participant will be sent this report in a secure text through the N1Thrive platform by our study team. Participants will also be sent links to several online videos explaining the terms and data visualizations available in their summary report. These videos will be general to the template report and will not contain any individual results or health information. Participants will be sent a satisfaction survey after receiving their individual report. Study participation will end upon completion of the satisfaction survey.

The satisfaction survey will be sent via text up to three times before a research coordinator will attempt to call individual participants to complete the satisfaction survey via phone.

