12. STATISTICAL ANALYSIS

- *Describe how your data will be used to test the hypotheses.*
- *State clearly what variables will be tested and what statistical tests will be used.*
- *Include sample size calculations.*
- *If this is a pilot study, state which variables will be examined for hypothesis generation in later studies.*

The sample size of 60 participants was chosen to have a sufficient number of patients to obtain a preliminary assessment of the feasibility of personalized trials of sleep quality with melatonin compared to a placebo. The numbers of sleep quality reports, questionnaires, and intervention repetitions per trial were based on expert recommendations by a statistician and estimations about maximal duration of the trial to maintain patient engagement. With n=60 randomized participants, expecting a trial completion rate of 70%, we anticipate SUS data are available in

about $n = 42$ participants, thus giving a standard error no greater than 8% in estimating the rate of SUS $\geq 85^{22}$. The standard error will be the largest when the trial completion rate is at 50%. Data will be reported transparently so that individual level heterogeneity can be assessed²³.

Participants will be randomized into one of two different intervention orders, ABCCBA or CBAABC, where A=3mg dose melatonin, B=.5mg dose melatonin, and C=placebo. Although participants will be aware of their randomization order (i.e. 'A' weeks, 'B' weeks, and 'C' weeks), they will be blinded to each letter's corresponding supplement or placebo until their participant summary report. Two intervention orders were chosen to test out the feasibility of carrying out a virtual, N-of-1 study. ABCCBA was chosen as an order to test participant acceptability with back-to-back single-blinded placebo intervention (i.e., no intervention) extending through 4 weeks. CBAABC was chosen as a companion intervention order to ABCCBA to test participant acceptability with starting a Personalized Trial with a single-blinded placebo after a baseline run-in (i.e., no intervention for the first 4 weeks). Intervention order was not included as a factor in the statistical analysis because this is an acceptability and feasibility study.

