- Mean Within-Subject Difference in Self-Reported Side Effects from Baseline, using the average number of days side effects were reported during treatment periods.
- Mean Within-Subject Difference in Device-Recorded Daily Steps from Mean Baseline, using participant Fitbit data
- Mean Within-Subject Difference in Device-Recorded Nightly Sleep from Mean Baseline, using participant Fitbit data

Other exploratory analyses include:

- Google and social media ad metrics
- Social media activity, including but not limited to:
 - Social media conversion rate, defined as total impressions compared to total click-through
 - Cost per social media conversion
- Website activity, including but not limited to:
 - Total number of website visits per traffic source
 - Website bounce rates

Mean user total time on website

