17. RISKS TO SUBJECTS

- *Describe any potential risks and discomforts to the subject (physical, psychological, social, legal, or other) and assess their likelihood and seriousness and whether side effects are reversible. Where appropriate, describe alternative treatments and procedures that might be advantageous to the subjects.*
- *Include risks to others , like sexual partners (if appropriate)*
- *Discuss why the risks to subjects are reasonable in relation to the anticipated benefits and in relation to the importance of the knowledge that may reasonably be expected to results*
- *Describe the procedures for protecting against or minimizing any potential risks, including risks to confidentiality, and assess their likely effectiveness.*

This study poses no greater than minimal risk to subjects. Monitoring for adverse side-effects will be performed during the N-of-1 trial. Subjects will be encouraged to adhere to the supplement protocol, but will also be told that they can discontinue intervention at any time.

Melatonin was selected for this study as a minimal-risk sleep quality intervention option that has been shown to be a safe and effective option for many people. Some people, however, may experience mild side effects from melatonin. The most common side effects are headache, dizziness, nausea and sleepiness²¹. Less common side effects include short-lasting feelings of depression, mild tremor, mild anxiety, abdominal cramps, irritability, reduced alertness, confusion or disorientation, and abnormally low blood pressure. There is a chance that participants could experience these side effects, however the chances are low given the duration and dosing proposed for this research^{24, 25}. Participants will be advised to neither drive nor operate heavy machinery within 5 hours of taking their nightly supplement. Participants will only be advised to take melatonin one hour before their bedtime. Study participants document side effects daily and may withdraw from the study at any time without consequence should these side effects be viewed as bothersome.

There is also the potential risk of loss of privacy of information pertaining to research material collected by the study. Yet, we will take precautions, described below, to minimize these risks.

Melatonin Adverse Events

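### As described, the daily side-effect item counts only pill-attributed symptoms, and its outcome is a change from a pill-free baseline at which no such question is described

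*Combined protocol and SAP*

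**What the plan says.** Section 11 (Research Procedures) describes the daily side-effect question in one sentence: "Morning surveys during the intervention weeks will also include questions about any melatonin or placebo-related side-effects the participant is experiencing". It gives no item wording, symptom list, instruction to report regardless of cause, or separate causality question. Section 17 (Risks to Subjects) adds only this: "Study participants document side effects daily".

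For the two baseline weeks, when no melatonin or placebo is supplied, Section 11 describes a different morning survey: "Each morning, baseline participants will receive a survey asking a few questions about their sleep quality the previous night using a modified version" of a sleep diary, plus factors that may have disturbed sleep. No side-effect question is mentioned.

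Section 12 (Statistical Analysis) lists one side-effect outcome among those analysed at the individual level: "Mean Within-Subject Difference in Self-Reported Side Effects from Baseline, using the average number of days side effects were reported during treatment periods". Section 11 puts side effects into the data compiled for the participant's report, which relates results to the 3 mg, 0.5 mg and placebo periods.

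On blinding, Section 12 says that participants know the letter of the bottle in use but "they will be blinded to each letter's corresponding supplement or placebo until their participant summary report". Section 3 counts harms information among the strengths of N-of-1 trials: "They also yield information on off-target actions, such as side-effects or unintended consequences".

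**The concern.** A crossover within one person establishes cause by comparing bottles. If the question asks the participant to decide cause first, the recorded count mixes two things: how often symptoms occur, and how often this person puts them down to the pill. Only the first is of interest. Several effects named in Section 17, such as irritability, sleepiness and reduced alertness, are also ordinary consequences of a bad night and easily explained away.

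The baseline adds a second problem. A count of pill-related effects has no meaning in weeks without a pill, yet the outcome is defined as a change from those weeks.

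At stake is the side-effect part of each participant's report, which that person may use to choose between bottles, and one of the secondary outcomes.

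**Working it through.** **Plan's own figure.** The plan gives no rate, power or precision for side effects, so there is nothing to reproduce. Its only precision figure concerns the SUS: sqrt(0.5 × 0.5 / 42) = 7.7%, consistent with the stated ceiling of 8%. It has no bearing here.

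**Inputs.**
- Mornings per condition: 2 periods × 14 = 28 (Section 11). Baseline: 14.
- Symptom-day rate s and probability a that a symptom is attributed to the pill: not in the documents. Assumed s = 10% to 30% and a = 0.2 to 0.6.

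**Formula**, if the item is worded as described: expected reported days = 28 × s × a.

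**1. Equal attribution, real difference.** The difference is multiplied by a.
- Assumed excess of 4 days: 4 × 0.3 = 1.2; 4 × 0.6 = 2.4.
- Assumed symptom days of 30% v 15%: 8.4 v 4.2, a true difference of 4.2 days. At a = 0.5 it shows as 2.1; at a = 0.2 as 0.84.

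**2. Unequal attribution, no true effect.** With s = 20%, symptom days are 28 × 0.20 = 5.6 on each bottle.

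| Attribution | Reported days | False difference |
|---|---|---|
| 0.3 v 0.3 | 1.68 v 1.68 | 0 |
| 0.4 v 0.3 | 2.24 v 1.68 | 0.56 |
| 0.6 v 0.3 | 3.36 v 1.68 | 1.68 |

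At 0.6 v 0.3, varying s gives 28 × 0.10 × 0.3 = 0.84 days and 28 × 0.30 × 0.3 = 2.52 days.

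**3. Unequal attribution, real effect.** For symptom days of 30% v 15%, attribution of 0.3 v 0.6 gives 8.4 × 0.3 = 2.52 and 4.2 × 0.6 = 2.52. The 4.2-day difference disappears.

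**4. Attribution that changes over time.** In both orders (ABCCBA and CBAABC) each condition has mean period position 3.5, so a linear drift cancels. Heightened attribution in period 1 alone (0.5, then 0.3; s = 20%) does not cancel. The bottle used first gets 14 × 0.2 × (0.5 + 0.3) = 2.24 days and the other two get 14 × 0.2 × (0.3 + 0.3) = 1.68. Averaged over equal groups, A and C are each (2.24 + 1.68) / 2 = 1.96 and B stays at 1.68. An individual report carries the full 0.56.

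**5. Baseline.** With s = 20% throughout and no effect of any pill, a two-week period at a = 0.3 yields 14 × 0.2 × 0.3 = 0.84 reported days. Baseline yields no data, or zero because there is no pill to blame. The change from baseline is then either not computable or +0.84 days with nothing happening. A cause-free item would give 14 × 0.2 = 2.8 days in each, a difference of 0.

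**6. What is already recorded without attribution.** Section 11 has momentary ratings of mood, stress, pain, fatigue, confidence and concentration three times a day, at baseline and on treatment. Against the Section 17 list, they leave out dizziness, nausea and abdominal cramps, for example, and reach headache and sleepiness only indirectly through pain and fatigue.

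**The case against.** The strongest objection is that the survey text is not in the documents. The Section 11 phrase may be a label for a checklist of known effects, or for anything felt while on study pills; it speaks of questions in the plural, and the Section 17 sentence carries no attribution filter. This stands, and it makes the point conditional. It does not dispose of it, because no section says that symptoms are recorded regardless of cause. If they are, the sponsor need only say so.

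Second, with an intact blind, beliefs about a bottle are unrelated to its content, so across participants the expected effect is shrinkage or noise, not a systematic false signal. This also stands. A reader might infer that the item will produce large spurious differences; attribution of 60% v 10%, for instance, would give 5.6 × 0.5 = 2.8 days. Nothing in the documents supports so wide a contrast, and 40% v 30% gives 0.56. The individual report remains exposed, because each letter is used in two periods and a belief formed in the first can carry into the second. Shrinkage needs no failure of the blind.

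Third, the momentary ratings already cover much of the ground without attribution. This narrows the gap but leaves the symptoms noted in the check.

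Fourth, a reader might infer that safety oversight rests on this count. It does not. Section 11 gives a phone number and email address with every survey, Section 16 provides for participants to contact the team, and Section 17 has the Principal Investigator review serious events and the DSMB review all adverse-outcome data.

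Fifth, asking about each of the 12 effects named in Section 17 plus an other category would mean 13 × 84 = 1,092 checks per participant over the intervention, in a study that measures usability and survey adherence. That is a fair objection to separate questions, less so to one select-all item.

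**Conclusion.** The point holds conditionally and is worth a small change. If the item is worded as Section 11 describes, the Section 12 count is symptom days multiplied by the chance of blaming the pill. Under equal attribution of 30% to 60%, an assumed 4-day excess shows as 1.2 to 2.4 days. Under unequal attribution with no true effect and symptoms on 20% of days, the false gap is 0.56 to 1.68 days for the contrasts of 40% v 30% and 60% v 30%, and zero if attribution is equal. These rates are assumptions, and the figures show the mechanism, not its likely frequency.

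The baseline inconsistency is firmer because it rests on the text alone: the change from baseline has either no baseline data or a baseline of zero by definition.

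The documents do not show that the actual survey filters by cause, that the comparison of bottles is biased in one direction, or that adverse-event oversight is compromised. The SUS primary outcome does not use this count.

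**What to change.** In Section 11, for both baseline and intervention weeks, give the text of one select-all-that-apply morning item. It should list the symptoms named in Section 17 that a participant can notice, plus other and none, and ask about them regardless of suspected cause. Low blood pressure should be left out, since a participant cannot observe it directly; that leaves 11 of the 12. A separate optional item may ask whether the participant thinks the pill was responsible.

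In Section 12, define the outcome as days with any listed symptom irrespective of attribution, compared between 3 mg, 0.5 mg and placebo and with baseline. Express it per two-week period, so that 14 baseline mornings and 28 per condition are on one scale. Show the attributed count as supportive only.

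If the existing item is already cause-free, stating its text and adding it at baseline would be enough for Section 11.

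The cost is a slightly longer survey on 98 mornings (14 + 84) and higher raw counts in every period, placebo included, which the participant report should explain.

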4. OBJECTIVE(S)/SPECIFIC AIMS AND HYPOTHESES

- *A concise statement of the goal(s) of the current study.*
- *The rationale for and specific objectives of the study.*
- *The goals and the hypothesis to be tested should be stated.*

We believe the delivery of N-of-1 methodology through Personalized Trials is feasible to scale to a large, randomized trial, and eventually to standard clinical practice. In order to demonstrate this feasibility, we must be able to collect data

illustrating that Personalized Trials can be a low-burden, satisfactory tool that can be scaled to individuals and clinicians.

We will additionally examine the novel individual-level heterogeneity of intervention effect and observed outcomes made possible by the N-of-1 trial design and will test the feasibility of pooling real-world N-of-1 results across patients to efficiently estimate the observed effect of non-prescription dietary supplements for poor sleep quality and thus the N-of-1 trial design.

Thus, the goals of this pilot study are to:

1. Conduct a pilot test (N=60) of a Personalized Trial that is delivered remotely to participants in the United States.
2. Collect data regarding minimum viable product (MVP) specifications for a future technology platform to deliver Personalized Trials.
3. Incorporate medication adherence device technology into an N-of-1 platform.
4. Elicit participant attitudes and opinions toward participating in a single-blinded protocol with use of a placebo arm in their Personalized Trial
5. Elicit participant attitudes and opinions toward using Personalized Trials to help inform their personal wellness strategy.

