9. STUDY TIMELINES

- *Describe the duration of an individuals participation in the study*
- *Describe the duration anticipated to enroll all study subjects*
- *The estimated date of study completion*

The study will take place over the course of 14 weeks. The first two weeks will be a baseline period, where no supplement is assigned, but data are collected, including self-report of sleep quality and duration and accelerometer-derived sleep and activity data. After successful completion of the baseline period, participants will be randomized to six 2-week intervention blocks of a 3mg dose melatonin, a 0.5mg dose melatonin, and a placebo. At the end of the 14 weeks, a report containing the individual's observed data will be prepared for each participant and electronically sent to them along with a satisfaction survey (electronic, or phone if they are non-responders). Creating this type of participant report will help to assess the feasibility of using a N-of-1 trial design through user-acceptability of sleep quality and wellness-related data visualizations and the ability to choose preferred intervention (if any) based on the data. This report will be sent within 3 months of study completion. A \$100 pay card (ClinCard) will be sent to each participant as compensation for their time after the successful completion of 14 weeks of data collection, satisfaction survey, and return of the Nomi smart bottles to the manufacturer. After the satisfaction survey is completed, study coordinators will reach out to each participant with an invitation to virtually interview them about their experience in Personalized Trials.

Potential participants will have the opportunity to provide preferences of start dates during their enrollment process. The study team will confirm applicability of the

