Partial withdrawal, defined as study participation and data collection without the use of one of the melatonin/placebo supplements will be allowed if a participant experiences an adverse event to one of the intervention options (3mg dose melatonin, 0.5mg dose melatonin, or placebo). In instances where participants contact the research team to self-report serious side-effects or otherwise contact the research team with concerns about their self-reported side effects, participants will be permitted to continue their involvement in the study, should they be interested. Participant data will continue to be collected and monitored, while removing the self-reported adverse intervention option from their randomized protocol (i.e. skip the intervention days and continue with placebo and/or other intervention). This will allow the participant to still evaluate their individual response to the self-reported non-aggravating intervention option. In the event that both intervention options create self-reported adverse events for the participant, they will be withdrawn from the study.]

Participants who are deemed ineligible and removed from the study during the intervention period (but not the baseline period) and participants who are withdrawn from the study will still be asked to complete the end-of-study satisfaction survey and follow-up interview. These participants will not receive a personalized participant report, and therefore the questions asked in the satisfaction survey and follow-up interview will be abbreviated (will not include the approved questions about the participant report asked of other participants).

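### Participants who receive a report are asked about the blinded placebo only with or after that report, and no pre-report placebo item or bottle guess is described

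*Combined protocol and SAP*

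**What the plan says.** Section 2 names the feasibility of using a placebo among the study's purposes. Goal 4 in section 4 is more specific: "Elicit participant attitudes and opinions toward participating in a single-blinded protocol with use of a placebo arm in their Personalized Trial". Section 12 justifies both intervention orders as tests of how acceptable blinded placebo is: four consecutive weeks of it in ABCCBA, and starting on it in CBAABC.

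On blinding, section 12 says of participants that "they will be blinded to each letter's corresponding supplement or placebo until their participant summary report". Section 11 describes the report as presenting the participant's data "in relation to the 3mg melatonin, 0.5mg melatonin, and placebo intervention periods". The report therefore gives the code and the results together.

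On timing, section 11 says: "Participants will be sent a satisfaction survey after receiving their individual report". Section 9 has the report "electronically sent to them along with a satisfaction survey (electronic, or phone if they are non-responders", which puts the two together. Both sections place the interview after the survey. Section 9 adds: "This report will be sent within 3 months of study completion".

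Section 16 covers people removed or withdrawn during the intervention, who are still asked for both the survey and the interview: "These participants will not receive a personalized participant report, and therefore the questions asked in the satisfaction survey and follow-up interview will be abbreviated".

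**The concern.** Goal 4 is about the experience of taking part under a blind. A participant who has read the report knows, or can know, which bottle was placebo and whether sleep on it was better, worse or no different. An opinion given then mixes the experience of blinded placebo with a reaction to the result. Someone who slept best on placebo and someone who slept worst on it may report different attitudes even if they felt the same while blinded.

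A guess of bottle content is a related matter. It means something only before the reveal, and the documents describe no point at which it is asked. Asking is worthwhile here because section 12 gives the letters the same meaning for every participant and says that coordinators are not blinded.

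At stake are goal 4 and the acceptability argument for the two orders. A later trial would have difficulty separating views on remote single-blinding from views on the outcome.

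**Working it through.** **1. Planned contacts set against the moment of unblinding (sections 9, 11, 12 and 16).**

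| Contact | Content described | Before the report? |
|---|---|---|
| Three texts a day | six momentary ratings | yes |
| Morning survey | sleep diary, side effects | yes |
| Sunday survey ending each period | includes the Insomnia Severity Index (ISI); other items not listed | yes |
| Smart bottles | melatonin and placebo adherence | yes |
| Report | data by 3 mg, 0.5 mg and placebo | this is the unblinding |
| Satisfaction survey | usability and satisfaction | no (with or after it) |
| Interview | experience and opinions | no (after the survey) |

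No contact before the report is said to ask about placebo, blinding or bottle identity.

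**2. The plan's own figures (section 12).** Expected completers: 60 × 0.70 = 42, as stated. Largest standard error of a proportion: √(0.5 × 0.5 / 42) = 0.077, within the stated 8%. Both reproduce, and neither is affected by this point.

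**3. Who answers in which state.** Completers asked with or after a report: about 42 of 60. Participants who could be asked without one: at most 60 − 42 = 18 (30%), all of them removed or withdrawn. In a two-by-two layout of completion against report, the cells for completers without a report and withdrawn participants with a report are empty by design. A difference in attitude between the two groups could come from knowing the result or from whatever led to withdrawal, and the data could not separate these. The plan also counts on SUS data from only about 42, the number of completers, so it does not rely on answers from the withdrawn.

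**4. Lag.** Assume that the 3-month limit runs from the participant's own week 14, and take 3 months as about 13 weeks. The longest gap between the last pill and the report is then about 13 weeks. For the placebo periods singled out by the two orders:
- ABCCBA: the placebo block ends at intervention week 8 of 12, so (12 − 8) + 13 = 17 weeks.
- CBAABC: the opening placebo block ends at intervention week 2, so (12 − 2) + 13 = 23 weeks.

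These are upper limits. A report sent promptly would shorten them.

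**5. What a guess would provide.** With three bottles, the chance of naming the placebo bottle at random is 1/3. With n = 42 the standard error is √((1/3 × 2/3) / 42) = 0.073, about 7 percentage points. That is adequate for a descriptive figure in a pilot.

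**The case against.** The case for leaving the plan as it is has several strands, and most of them limit the point.

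- **The instruments are not in the documents.** The Sunday survey is said only to include the ISI, and the survey and interview questions are not reproduced. A reader might infer that bottle guesses are never recorded. The documents support only that none is described. This stands.
- **Some participants are asked without a report.** A reader might infer that everyone answers unblinded. Section 16 shows otherwise, so the point is confined to those who receive a report. The plan proposes no comparison of the two groups; the confounding matters only if the withdrawn participants' answers are used to supply the blinded view.
- **There is blinded evidence on placebo.** Section 12 lists placebo adherence as a secondary outcome, recorded by the bottle during the blinded weeks. It bears on the feasibility purpose in section 2, but it measures behaviour and goal 4 asks for attitudes.
- **Views after the report are legitimate.** The personalized trial includes the reveal, and a blinded person cannot comment directly on placebo weeks that they cannot identify. This stands, and is why the later questions should stay. It does not make them a substitute for the earlier ones.
- **A guess rate is ambiguous.** A correct guess after 12 weeks may reflect felt benefit or side effects and need not mean that concealment failed. A reader might infer that a guess would settle whether the blind works, or that the sleep contrasts are shown to be biased. Neither follows. Those contrasts are secondary and feed the participant report, and section 23 says the study is not designed to document benefit.

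**Conclusion.** The point holds for participants who receive a report, about 42 of 60 if completion is 70% and every completer receives one. For them the only described instruments for goal 4 come with or after the unblinding, up to about 3 months after the study ends. Their answers can be coloured by the result, and the few people asked without a report are all withdrawals.

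It would be too strong to say that goal 4 cannot be answered. Post-report opinions are part of the answer, and the documents give no evidence on how far the result shifts them. The missing piece is the view held while still blinded, which cannot be collected later. The SUS primary endpoint, its standard error and the adherence outcomes are unaffected. This is a cheap improvement, not a flaw in the primary analysis. It rests on the survey content as described; if the unseen instruments already contain such items, all that remains is to say so in the protocol.

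**What to change.** In the Sunday survey that already ends period 6, before any report is released, add:

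- (a) a guess of the content of bottles A, B and C, with confidence and the reason for the guess (for example felt benefit, side effects, other);
- (b) a few short items on the acceptability of the blinding and of possibly taking placebo.

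Put the same items in the abbreviated survey already planned for withdrawn participants, before any unblinding. Repeat (b) after the report. For goal 4, present pre-report and post-report answers separately, and the guess rate as descriptive only.

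Leave the SUS after the report, because section 12 defines it as covering the system through receipt of the report. A stated bottle preference before the report is not needed; if the team wants one it should be optional, since it could anchor the later choice. Sections 9 and 11 should be reconciled on whether the survey goes out with the report or after it.

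The cost is a few extra items and a change to survey content. Completers need no new contact and no additional text survey, so the limit of five survey texts a day in section 11 still holds. Guessing may prompt people to think about bottle identity, but only at the end of the last period.
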